5. ENDPOINTS

5.1 PRIMARY ENDPOINTS

Primary endpoints are defined in Section 2.1.2 of the CTP.

5.2 SECONDARY ENDPOINTS

5.2.1 Key secondary endpoints

Not applicable, as no key secondary endpoint was specified in the CTP.

5.2.2 Secondary endpoints

The secondary endpoint is defined in Section 2.1.3 of the CTP.

5.3.1 Safety parameters

Safety will be assessed based on the following further parameters of interest:

- AEs (including clinically relevant findings from the physical examination)
- Safety laboratory tests
- Vital signs (blood pressure, pulse rate)
- Spirometry
- Clinically relevant findings from physical examination, 12-lead ECG. and echocardiography (as part of AE analysis)

Marked changes in vital signs will be defined as follows.

A marked increase is defined as:

- Systolic Blood Pressure >150 mmHg and increase >=25 mmHg above baseline
- Diastolic Blood Pressure >90 mmHg and increase >10 mmHg above baseline
- Pulse Rate >100 bpm and increase >10 bpm above baseline

A marked decrease is defined as:

- Systolic Blood Pressure <100 mmHg and decrease >10 mmHg below baseline
- Diastolic Blood Pressure <60 mmHg and decrease >10 mmHg below baseline
- Pulse Rate <60 bpm and decrease >10 bpm below baseline

6. GENERAL ANALYSIS DEFINITIONS

6.1 TREATMENTS

For basic study information on the treatments to be administered and selection of dose, cf. Section 4 of the CTP. All patients will undergo two treatment periods in a fixed sequence.

Each patient is planned to be treated in two subsequent treatment periods. In the first treatment period, patients will receive a single dose of Microgynon® (30 mcg ethinylestradiol and 150 mcg levonorgestrel; reference treatment, R). In the second treatment period, patients will receive a single dose of Microgynon® after continuous intake of a stable dose of nintedanib (150 mg b.i.d. or 100 mg b.i.d.) for at least 10 consecutive days (test treatment, T). Nintedanib treatment will be continued for at least 14 days to approximately 28 days in this trial. The sequence of these treatment periods is fixed and the same for all patients.

Microgynon® intake in the first treatment period will be at least 3 days before first nintedanib intake in the second treatment period.

For statistical analysis of AEs and vital signs, and for listings of safety laboratory, study phases are defined for each patient as described in [Table 6.1: 1](#) and [Table 6.1: 2](#). Note that only the date of AE onset is reported in the eCRF, but not the clock time.

Table 6.1: 1 Flow chart of analysis phases for statistical analyses of AEs and vital signs

Study analysis phase	Label	Start (included in phase)	End (excluded from phase)
Screening	Screening	Date of informed consent	Date of first administration of study drug
On-treatment microgynon	MIC	Date of administration of microgynon in Treatment Period 1 I.e., the day of administration of microgynon is included in this phase.	Day of end of REP (3 days) of microgynon: Date of administration of microgynon in Treatment Period 1 + 3 days I.e., the day of end of REP is excluded from this phase.
			OR
			Date of first administration of nintedanib in Treatment Period 2 (whichever occurs first).
Follow-up microgynon	FUP-MIC	Date of administration of microgynon in Treatment Period 1 + 3 days	Date of first administration of nintedanib in Treatment Period 2 This phase does not exist, if start \geq end.
On-treatment nintedanib loading phase	Loading NIN	Date of first administration of nintedanib in Treatment Period 2	Date of administration of microgynon in Treatment Period 2
On-treatment nintedanib plus microgynon	NIN+MIC	Date of administration of microgynon in Treatment Period 2 I.e., the day of administration of microgynon is included in this phase.	Day of end of REP (3 days) of microgynon: Date of administration of microgynon in Treatment Period 2 + 3 days I.e., the day of end of REP of microgynon is excluded from this phase.

Table 6.1: 1 Flow chart of analysis phases for statistical analyses of AEs and vital signs (continued)

Study analysis phase	Label	Start (included in phase)	End (excluded from phase)
On-treatment nintedanib	NIN	Date of administration of microgynon in Treatment Period 2 + 3 days	Day after last contact date OR If patient is reported to continue into the 1199-0225 rollover study: Day after day of End of Treatment visit (which will be done simultaneously to End of Study visit) This phase does not exist, if start \geq end.

CTR Section 15, Appendix 16.1.13.1.8.2 and Appendix 16.1.13.1.8.3 AE displays will present results for the on-treatment phases "MIC", "Loading NIN", "NIN+MIC", and "NIN" only. Screening and FUP-MIC will not be included in this analysis. CTR Section 15 AE displays (but not Appendix 16.1.13.1.8.2 and Appendix 16.1.13.1.8.3 AE displays) will additionally present the following totals:

- "**Total NIN**", defined as the total over on-treatment phases involving nintedanib, i.e. "Loading NIN" + "NIN+MIC" + "NIN".
- "**Total on-trt**", defined as the total over all on-treatment phases, i.e., "MIC" + "Loading NIN" + "NIN+MIC" + "NIN".

CTR Appendix 16.1.13.1.8.1 displays will present results for all study analysis phases defined in [Table 6.1: 1](#) above, and will additionally present the following totals:

- "**Total NIN**", defined as the total over on-treatment phases involving nintedanib, i.e. "Loading NIN" + "NIN+MIC" + "NIN".
- "**Total**", defined as the total over all study analysis phases.

Table 6.1: 2 Flow chart of analysis phases for statistical analyses of safety laboratory

Study analysis phase	Label	Start (included in phase)	End (excluded from phase)
Screening	Screening	Date of informed consent	Date/time of first administration of study drug
On-treatment microgynon	MIC	Date/time of administration of microgynon in Treatment Period 1	Date/time of administration of microgynon in Treatment Period 1 + REP (72 h)
			OR
			Date/time of first administration of nintedanib in Treatment Period 2
			(whichever occurs first).
Follow-up microgynon	FUP-MIC	Date/time of administration of microgynon in Treatment Period 1 + REP (72 h)	Date/time of first administration of nintedanib in Treatment Period 2
On-treatment nintedanib loading phase	Loading NIN	Date/time of first administration of nintedanib in Treatment Period 2	Date/time of administration of microgynon in Treatment Period 2
On-treatment nintedanib plus microgynon	NIN+MIC	Date/time of administration of microgynon in Treatment Period 2	Date/time of administration of microgynon in Treatment Period 2 + REP (72 h)
On-treatment nintedanib	NIN	Date/time of administration of microgynon in Treatment Period 2 + REP (72 h)	12:00 a.m. on day after last contact date

More details on the technical implementation of these analyses are provided in the Analysis Data Set (ADS) Plan of this TSAP.

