In Table 6.1: 1 of the initial TSAP, a nintedanib follow-up phase was defined, which is not in accordance with the definition quoted above. Therefore, the nintedanib follow-up phase was not adopted by this final TSAP and the definition of the on-treatment nintedanib phase was adapted to match the definition quoted above.

Further changes compared to the initial TSAP:

- Definition of further safety parameters of interest was added to [Section 5.3.1](#).
- Baseline parameters were added to list of baseline characteristics in [Section 5.4.1](#), respective analyses were added to [Section 7.1](#).
- Definition of nintedanib treatment compliance was added to [Section 5.4.2](#) and its presentation was specified in [Section 7.3](#).
- Definition of nintedanib treatment exposure was revised in Section 5.4.2.
- Definition of AE analysis phases in [Table 6.1: 1](#) and definition of AE collapsing in [Section 7.8.1](#) were adapted to the decision that clock time will not be collected in the eCRF.
- Definition of analysis phases in [Section 6.1](#) was restricted to AE, vital signs and laboratory data, will not be needed for spirometry.
- [Table 6.2: 1](#) was added to specify which important PDs could potentially lead to exclusion from which analysis set.
- Definition of an enrolled set was added to [Section 6.3](#).
- Analyses of AEs by safety topic were added to Section 7.8.1.
- Descriptive analysis of vital signs were added to [Section 7.8.3](#).
- Presentation of pregnancy test results was added in [Section 7.8.5.5](#).
- A few additional clarifications were added, text was adapted to the new BI standard process (e.g., use of a decision log to capture RPM decisions).

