6.7 BASELINE, TIME WINDOWS AND CALCULATED VISITS

Baseline is defined as the last value prior to first administration of study drug.

Time windows are defined in Section 6.1 of the CTP. Adherence to time windows will be checked at the RPM.

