7. PLANNED ANALYSIS

The format of the listings and tables will follow the BI guideline "Reporting of clinical trials and project summaries" (001-MCG-159) (9).

The individual values of all patients will be listed by patient number and visit (if visit is applicable in the respective listing). Listings will also show treatment sequence, although all patients received treatments in the same sequence. AE listings will be sorted by assigned treatment (see [Section 7.8.1](#) below for details). The listings will be contained in Appendix 16.2 of the CTR.

The following standard descriptive statistical parameters will be displayed in summary tables of continuous variables:

N	number of non-missing observations
Mean	arithmetic mean
SD	standard deviation
Min	minimum
Median	median
Max	maximum

For plasma concentrations as well as for all PK parameters, the following descriptive statistics will additionally be calculated:

CV	arithmetic coefficient of variation
gMean	geometric mean
gCV	geometric coefficient of variation

Moreover, the 10th, 25th, 75th and 90th percentiles will be also presented in Section 15.6.2 for the descriptive statistics of the PK parameters.

The data format for descriptive statistics of plasma concentrations will be identical with the data format of the respective concentrations. The descriptive statistics of PK parameters will be calculated using the individual values with the number of decimal places as provided by the evaluation program. Then the individual values as well as the descriptive statistics will be reported with three significant digits in the CTR.

Tabulations of frequencies for categorical data will include all possible categories and will display the number of observations in a category as well as the percentage (%) relative to the total number of patients. Percentages will be rounded to one decimal place. The category missing will be displayed if and only if there are actually missing values. Percentages will be based on all patients in the respective patient set whether they have non-missing values or not.

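### SAP Table 6.1: 1 applies the adverse-event date rule to vital signs, so the pre-dose Visit 6 reading, taken on nintedanib alone, is labelled NIN+MIC (minor; descriptive safety output only)

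*SAP*

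**What the plan says.** **SAP.** Section 6.1 sets the scope: "For statistical analysis of AEs and vital signs, and for listings of safety laboratory, study phases are defined for each patient". Section 4 confirms that vital signs were kept in deliberately; the phase definition "was restricted to AE, vital signs and laboratory data, will not be needed for spirometry".

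Table 6.1: 1 covers adverse events and vital signs and uses calendar dates. Loading NIN runs from the date of first nintedanib up to, but not including, the date of the second Microgynon tablet. NIN+MIC starts on that date, and "the day of administration of microgynon is included in this phase". (The same sentence also stands in the MIC row for Period 1; the NIN+MIC row is the one that matters for Visit 6.) NIN+MIC closes three days later, when "the day of end of REP of microgynon is excluded from this phase". The only reason Section 6.1 gives for working in dates is that the eCRF holds no clock time for adverse-event onset. It says nothing of this kind about vital signs.

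Table 6.1: 2, for safety laboratory data, works in date and time. Its Screening phase, for example, ends at "Date/time of first administration of study drug".

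Section 6.7 fixes the baseline: "Baseline is defined as the last value prior to first administration of study drug". Section 7.8.3 plans summaries of observed values and changes from baseline, and frequencies of marked changes. It does not say whether they are by phase or by visit.

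**Protocol.** The Flow Chart schedules vital signs at Visits 1, 2 and 6, EOT and FU only. The PK-day overviews list vital signs and safety laboratory tests as pre-dose at Visits 2 and 6. Section 5.2.2 also places vital signs ahead of blood sampling, and the first PK sample is at -00:35.

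**The concern.** At Visit 6 the patient has taken nintedanib for at least 10 days, and the first tablet's 3-day residual effect period has long passed. The second tablet has not been swallowed. A whole-day date rule nevertheless files this reading under the combination. Laboratory tests from the same pre-dose block are filed under nintedanib alone, so one SAP gives two labels to one moment.

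If the vital-sign summaries are tabulated by phase, every scheduled Visit 6 change or marked change appears under NIN+MIC and none under Loading NIN. A reader could credit to co-administration a change that was already present on nintedanib alone. Protocol Section 1.2.1 lists hypertension among the effects associated with nintedanib, and SAP Section 5.3.1 defines marked blood-pressure increases as an output, so the row would be looked at.

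SAP Section 4 also recognises, for laboratory data, that no sample falls within the Microgynon residual effect period, and doubts the value of a descriptive comparison for that reason among others. The vital-sign schedule has the same limit, but the descriptive vital-sign analyses added in the final SAP carry no such note.

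**Working it through.** The plan states no figure to reproduce. The check applies both phase rules to each scheduled reading of one patient who follows the visit schedule.

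**Inputs**
- Scheduled vital signs: Visits 1, 2, 6, EOT, FU (Flow Chart).
- First tablet: Day -3, 08:00. First nintedanib: Day 1, taken as 08:00. Second tablet: Day 11, 08:00 (Flow Chart and PK-day overviews).
- Visit 2 and Visit 6 readings: assumed at 07:20, i.e. 40 minutes before the tablet and before the 07:25 PK sample. Any pre-dose time on the same date gives the same labels.
- EOT: Visit 6 + 3 days, assumed at 09:00, i.e. 3 × 24 h + 1 h = 73 h after the second tablet. FU: 7 days after EOT.
- Microgynon residual effect period: 3 days (72 h in Table 6.1: 2).

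**Rules**
- Date rule (Table 6.1: 1): compare the calendar date of the reading with the dates of dosing; a phase includes its start date and excludes its end date.
- Date/time rule (Table 6.1: 2): the same comparison with clock times.

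**Steps for the two pre-dose readings**
- Visit 6, date rule: Day 11 is not before Day 11, so the reading is outside Loading NIN. It is before Day 11 + 3 = Day 14, so it is NIN+MIC.
- Visit 6, date/time rule: Day 11 07:20 is before Day 11 08:00, so it is Loading NIN.
- Visit 2, date rule: Day -3 is the start date of MIC, so it is MIC.
- Visit 2, date/time rule: Day -3 07:20 is before Day -3 08:00, so it is Screening.

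| Reading | Table 6.1: 1 (date) | Table 6.1: 2 (date/time) |
|---|---|---|
| Visit 1 | Screening | Screening |
| Visit 2, pre-dose | MIC | Screening |
| Visit 6, pre-dose | NIN+MIC | Loading NIN |
| EOT | NIN | NIN |
| FU | NIN | NIN |

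With Visit 6 moved to Day 25 the table is the same, because the labels at Visits 2 and 6 depend only on the reading and the tablet sharing a date.

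Under the date rule Loading NIN therefore has 0 scheduled readings, and the only scheduled reading in NIN+MIC precedes the combination. The Visit 2 label is uninformative rather than misleading: that reading is normally the baseline itself, so its change is zero by construction.

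**Size.** One potentially misleading label per patient who reaches Visit 6:
- completer who rolls over, no FU: 1/4 = 25% of scheduled readings;
- patient with FU: 1/5 = 20%.

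The safety analysis uses the treated set, whose size is not fixed. If only the 14 planned evaluable patients reach Visit 6, the count is 14 readings out of 14 × 4 = 56 to 14 × 5 = 70. If all of the approximately 24 enrolled patients did, it would be 24 out of 24 × 4 = 96 to 24 × 5 = 120. The upper end is a ceiling, since 24 already allows for drop-outs and interfering co-medication.

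**The case against.** The strongest reply is that harm is not shown. The phase displays spelled out in Section 6.1 are introduced as adverse-event displays, and Section 7.8.3 does not say by phase. Section 7 states that "The individual values of all patients will be listed by patient number and visit". Section 6.1 also says that "More details on the technical implementation of these analyses are provided in the Analysis Data Set (ADS) Plan of this TSAP", and that plan is not among the documents. This stands, and it makes the consequence conditional. It does not remove the rule: Section 6.1 says that the phases serve the statistical analysis of vital signs, and the SAP states no other assignment.

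Second, even by phase nothing is lost or mixed. For a patient on schedule, the NIN+MIC row is simply the Visit 6 data under another name. That is true, and it is why the point is minor.

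Third, the date rule has a coherent rationale. A clinically relevant vital-sign finding is reported as an adverse event, and one rule keeps the reading and that event in the same phase. This also stands as a trade-off. The SAP already accepts the opposite outcome for laboratory data.

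Stronger readings are tempting but unsupported:
- A reader might infer that a nintedanib blood-pressure signal would be hidden. It would not: NIN+MIC still names nintedanib, and the patient is on it under either label.
- A reader might infer that the MIC label at Visit 2 corrupts the baseline. Section 6.7 defines the baseline by first administration of study drug, independently of phase.
- A reader might blame this rule for the lack of post-dose vital signs within the Microgynon residual effect period. That comes from the protocol schedule.

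**Conclusion.** The point holds as a minor labelling fault in descriptive safety output. As written, the Visit 6 reading carries a treatment label that the protocol schedule contradicts, in 20% to 25% of a patient's scheduled readings; these shares count labels and do not measure bias. The PK endpoints, change-from-baseline values, marked-change definitions and by-visit listings are unaffected.

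The label assignment rests on the text of Table 6.1: 1 and on vital signs being taken pre-dose as scheduled. The consequence rests on a further assumption, that the Section 7.8.3 summaries are tabulated by phase. The counts assume one Visit 6 profile per patient; a repeated PK profile could add a reading.

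**What to change.** Preferred: state in Section 7.8.3 that vital-sign summaries are presented by planned visit. No phase label is then attached to the reading.

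If phases are wanted, add an exception in Section 6.1. By planned visit, assign the scheduled pre-dose Visit 2 reading to Screening/baseline and the scheduled pre-dose Visit 6 reading to Loading NIN. Leave all other readings, including unscheduled ones, under the existing date rule: an unscheduled reading on a tablet day cannot be placed before or after the dose without a clock time.

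In either case, add a footnote that no vital signs are scheduled post-dose within the Microgynon residual effect period. Under the exception, MIC and NIN+MIC have no scheduled reading, and the footnote explains why. If the ADS Plan already contains such a rule, it need only be stated in the SAP.

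Cost: two or three sentences and one programming rule, with no new data. The phase option has one downside: an adverse event arising from a Visit 6 reading stays in NIN+MIC under the date rule while the reading moves to Loading NIN.

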6.2 IMPORTANT PROTOCOL DEVIATIONS

Data discrepancies and deviations from the CTP will be identified for all patients in the entered set, as defined in Section 7.3 of the CTP.

Consistency check listings (for identification of deviations from time windows) and a list of protocol deviations (e.g. deviations in drug administration, in blood sampling times, etc.) will be provided to be discussed at the report planning meeting (RPM). At this meeting, it will be decided whether a discrepant data value can be used in analyses or whether it must be corrected in the clinical database. Each protocol deviation must be assessed to determine whether it is an important protocol deviation (PD). For definition of important PDs, and for the process of identification of these, refer to the Boehringer Ingelheim (BI) reference document "Integrated Quality and Risk Management Process" (2).

If any important PDs are identified, they are to be summarised into categories and will be captured in the decision log and DV domain specification sheet (11). Categories which are considered to be important PDs in this trial are defined in the integrated quality and risk

management plan (IQRMP). If the data show other important PDs, the definition in the IQRMP will be supplemented accordingly by the time of the RPM.

Important PDs will be summarized and listed. [Table 6.2: 1](#) below specifies which kind of important PDs could potentially lead to exclusion from which analysis set. The decision on exclusion of subjects from analysis sets will be made at the latest at the Report Planning Meeting, after discussion of exceptional cases and implications for analyses. If the data show other important PDs, this table will be supplemented accordingly by the time of the Report Planning Meeting.

Table 6.2: 1 Handling of important PDs

PD code	PD Category & Brief Description	Excluded from which analysis set
A1.01 – A1.08	Inclusion Criteria Not Met	PKS
A2.01 – A2.26	Exclusion Criteria Violated	PKS
B1	Informed consent not available/not done	TS, PKS
B2	Informed consent too late	None
C1	Incorrect trial medication taken (i.e., deviation from the correct intended medication)	PKS
C2	Incorrect dose of trial medication taken	PKS
C3	Patient did not continuously take at least 10 consecutive days of a stable dose of nintedanib (b.i.d.) prior to the PK visit assessments in Period 2 (Visit 6)	PKS
C4	The patient missed one (or more) nintedanib capsules in the 3 days prior to or during PK profiling at Visits 6, 7, 8	PKS
D1	Prohibited medication use (cf. CTP Table 4.2.2.1:1)	PKS
D2	Improper washout of concomitant medication (cf. CTP Table 4.2.2.1:1)	PKS
G1	Incomplete intake of meal. Or non-adherence to dietary restrictions (cf. CTP Section 4.2.2.3)	PKS
G2	Treatment compliance not in accordance with protocol definition (cf. CTP section 4.3)	None

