4.3 TREATMENT COMPLIANCE

Patients will be asked to take their nintedanib medication as instructed by their treating physician. They shall be asked to report any instances when they could not take nintedanib as prescribed. The trial site will document the intake of nintedanib medication and provide an explanation in case the number of capsules expected to be taken differs from the actual number.

At clinic visits, Microgynon[®] (in Period 1) and Microgynon[®] together with nintedanib (in Period 2) will be administered under the supervision of the treating physician or trial staff to whom this task was delegated. The intake of both Microgynon[®] and nintedanib will be documented in the eCRF. During the phone contact 5A, after 9 days of nintedanib intake and one day prior to Visit 6 and also at Visit 6, the patient's treatment compliance will be checked using the PK Diary information filled in by the patient and also an overall drug accountability check will be done to verify if the patient took the required number of capsules consistent with a twice daily intake during the last 10 days prior to Visit 6.

In the following situations the PK Visit 6 must be postponed, because the nintedanib treatment intake will not be considered continuous or compliant and might affect the PK analysis for this trial:

- The patient did not continuously take at least 10 days of a stable dose of nintedanib (b.i.d.) prior to the PK visit assessments in Period 2, due to interruption or dose reduction of nintedanib, because of an AE or other reason.
- The patient missed two (or more) nintedanib capsules in the first 7 days.
- The patient missed one (or more) nintedanib capsules in the 3 days prior to (which can be checked on the PK Diary) and during the PK days in Period 2.

Patients will also be asked to adhere to the dietary restrictions.

Patients are requested to bring all remaining trial medication including empty package material with them when attending visits.

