7.3 TREATMENT COMPLIANCE

Nintedanib treatment compliance [%] and the assessment of whether the patient was compliant according to the protocol (yes/no, additional specification if no), will be listed as reported by the investigator in the eCRF. A footnote will explain that, in case of a treatment interruption, the compliance could be low (e.g. less than 80%) although the patient was compliant with the protocol.

Any deviations from complete intake will be addressed in the RPM (cf. [Section 6.2](#)) and described in the CTR.

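### Does SAP Table 6.2: 1 leave open whether a patient who missed two or more capsules in the first 7 days stays in the PK set?

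*SAP*

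**What the plan says.** Protocol section 4.3 names three situations in which "the PK Visit 6 must be postponed, because the nintedanib treatment intake will not be considered continuous or compliant and might affect the PK analysis". They are:

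1. fewer than 10 days of continuous stable dosing, because of an interruption or dose reduction;
2. "The patient missed two (or more) nintedanib capsules in the first 7 days";
3. one or more capsules missed in the 3 days before, or during, the PK days.

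SAP section 6.2, Table 6.2: 1, links deviation codes to analysis sets. C3 reads "Patient did not continuously take at least 10 consecutive days of a stable dose of nintedanib (b.i.d.) prior to the PK visit assessments" and is marked PKS. C4 restates the third situation and is also marked PKS. G2 reads "Treatment compliance not in accordance with protocol definition (cf. CTP section 4.3" and is marked None.

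The text above the table presents these as deviations that may lead to exclusion. It adds that the decision "will be made at the latest at the Report Planning Meeting, after discussion of exceptional cases and implications for analyses". SAP section 7.3 says of compliance: "Any deviations from complete intake will be addressed in the RPM". Both documents place the definitions of important deviations in the Integrated Quality and Risk Management Plan (IQRMP), which is not among the documents reviewed.

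**The concern.** Two of the three situations have a specific row and the middle one does not, and two codes with opposite consequences can reach it. G2 cites section 4.3 as a whole, with no wording that sets aside what C3 and C4 already cover; under G2 the patient stays in. C3 turns on continuous intake, and the protocol's own lead-in denies that word to all three situations: "because the nintedanib treatment intake will not be considered continuous or compliant and might affect the PK analysis for this trial". C3 also omits the protocol's reference to interruption or dose reduction, so its wording is wide enough to take in missed capsules. Under C3 the patient is a candidate for exclusion.

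The PKS carries the primary analysis of an open-label trial with about 14 evaluable patients. Neither document says that the Report Planning Meeting precedes sight of the PK results. If it did not, the choice of code could be made with the patient's ratio already known.

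**Working it through.** **Setting the texts side by side**

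| Protocol 4.3 situation | Specific row | General row |
|---|---|---|
| 1. Under 10 days of continuous stable dosing | C3 (PKS) | G2 (None) |
| 2. Two or more capsules missed, first 7 days | none | G2 (None) |
| 3. One or more capsules missed, 3 days before or during PK days | C4 (PKS) | G2 (None) |

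Reading specific rows before general ones, situations 1 and 3 go to C3 and C4, and G2 keeps the remainder. Of the listed situations, only the second remains. Two features of the texts support this.

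- The second situation starts at two capsules, so one capsule missed in that window does not trigger it. Continuous intake therefore cannot simply mean that no capsule was missed.
- If C3 covered any missed capsule in the 10 days, the part of C4 about the 3 days before the visit would be redundant.

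**The 7-day window.** The protocol does not anchor it. It checks that the capsule count is "consistent with a twice daily intake during the last 10 days prior to Visit 6", so the window may be the first 7 of those 10 days, or Days 1 to 7 of nintedanib. With Visit 6 on Day 11 the last 10 days are Days 1 to 10, and the two readings coincide. With Visit 6 on Day 25 the last 10 days are Days 15 to 24, and the first 7 of them are Days 15 to 21. Capsules missed on Days 1 to 7 would then precede a full 10-day run, and only G2 could apply.

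**Size if a case occurs.** Inputs from protocol section 7.7: gCV 20% (15% was seen for AUC), 14 evaluable patients, two-sided 90% interval, 95% tolerance probability. Assumption: 1 or 2 patients are affected, since no rate is given.

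First, the protocol's own precision (upper limit / point estimate):

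exp{ t(0.95, n−1) × √ln(1+gCV²) × √(2/n) × √[χ²(0.95, n−1)/(n−1)] }

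- n = 14: exp(1.771 × 0.1980 × 0.3780 × 1.3116) = exp(0.1739) = 1.190, as stated in Table 7.7: 1.
- The other rows also reproduce: 1.305 (n = 8), 1.249 (10), 1.214 (12), 1.172 (16).
- n = 13, which is not tabulated, gives 1.201.

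Next, the chance shift in the estimate when k of 14 pairs are dropped and these patients do not truly differ from the rest. The SD of one patient's log ratio is √(2 ln 1.04) = 0.280 at gCV 20% and √(2 ln 1.0225) = 0.211 at 15%. The SD of the shift is that figure × √(1/(14−k) − 1/14), and the 95% range is exp(±1.96 × SD).

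| gCV | k | SD of shift | 95% range |
|---|---|---|---|
| 20% | 1 | 0.0208 | 0.960 to 1.042 |
| 20% | 2 | 0.0306 | 0.942 to 1.062 |
| 15% | 1 | 0.0156 | 0.970 to 1.031 |
| 15% | 2 | 0.0230 | 0.956 to 1.046 |

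Last, dilution if two such patients are kept and the true ratio is 0.80. If they show half the effect on the log scale, the expected ratio is 0.80^(13/14) = 0.813. If they show none, it is 0.80^(12/14) = 0.826.

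These figures treat exclusion as loss of the whole pair. Under protocol section 7.3 a single parameter from one period keeps a patient in the PKS, and the Period 1 profile comes before any nintedanib. The practical question may therefore be only whether the Period 2 parameters are used. With subject as a random effect a lone Period 1 value can still contribute a little, so the figures are approximate.

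**The case for a change.** The strongest case for a change is that a deviation table exists to say in advance which patients are at risk of exclusion, and here it does not. Nothing in the SAP calls G2 the residual row. The 7-day and 3-day limits add up to the 10-day window, so both can be read as spelling out what continuous intake means, which favours C3. The protocol itself says that such intake may affect the PK analysis. A few words in one table would settle the matter before any result is seen.

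Part of this stands. The C3 reading is possible, the overlap in wording is real, and the order of the meeting and the PK results is not stated. Protocol section 7.3 does separate deviations, settled no later than the meeting, from non-evaluability found during data analysis. That suggests a separate step but does not prove the order.

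What does not stand is that the code would decide the outcome. A case coded C3 could still be kept after discussion, and a meeting decision is the design for every row. Timing relative to the PK results is likewise a question about all PKS exclusions, not about this row. The IQRMP may already settle the coding, which cannot be checked here.

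**Conclusion.** No change is needed. This is a gap in wording that the trial team can fill sensibly. The natural reading places the case under G2, the other reading is defensible, and SAP section 7.3 already sends any incomplete intake to the Report Planning Meeting. No stated rule is shown to give a wrong result. Rewording G2 would record a choice the meeting makes anyway, and would narrow its discretion for one rare case without removing it.

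The case needs two failures: the missed capsules, and a Visit 6 that went ahead despite required postponement and compliance checks at the telephone contact the day before and at the visit. If it happened in 1 or 2 of 14 patients, the chance movement in the ratio would be at most about 4% or 6% either way (95% range, gCV 20%). Precision would be no worse than the 1.214 that the protocol accepts for 12 patients. Dilution of a true 0.80 would reach 0.83 only if both patients showed no effect at all. The trial makes no confirmatory test, so no pass or fail decision turns on it.

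This rests on the assumed 1 or 2 patients, on the pair-deletion approximation, and on the IQRMP not saying something contrary.
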